#### Step 2 option 2: Multiple imputation at the weekly level

The simple imputation based on weekly mean SFDs may result in biased estimates if the data are missing for more than 10% of the participants or have a large proportion of missing weeks (Eekhout et al., 2014). After evaluation of the missing proportion and pattern, multiple imputations could be used. If the caregiver fails to submit the weekly survey or no information was provided for seven days of the week, the SFDs of the week will be coded as missing. The multiple imputation will be conducted at a weekly level. The number of missing observations ranges from 0 to 24 weeks. Multiple imputation will be used to predict how many SFDs per week by the selected observed weeks based on 1) the correlations between the missing weeks and other observed weeks; and 2) the duration of the bronchiolitis symptoms (number of weeks to be included). Multivariate Imputation by Chained Equations (MICE) R package (van Buuren & Groothuis-Oudshoorn, 2011) or MI procedure in SAS software (SAS Institute Inc., 2015) will be used. The imputation process will be repeated for at least 10 times at the weekly level (Stuart et al., 2009), after which the total SFDs across 24 weeks will be calculated by adding up the observed and imputed weekly SFDs for every imputed data set. Each of the imputed data sets will be analyzed using a mixed effect model, and the parameter estimates will be combined from all analyzed data sets at the pooling phase.

#### **Secondary endpoint 1 unscheduled healthcare visits (UHV):**

For the secondary endpoint 1 of UHV, if the missing data are caused by missed submission of the weekly survey or reporting the counts of the visits for a caregiver, the AE reports will be used as resources to calculate the number of visits during the missing weeks. The number of unscheduled healthcare visits of the missing week will not be imputed using a statistical algorithm since the imputation may overestimate the number of visits if there is no information in the AE reports about hospitalizations, ER, or other medical care visits.

#### **Secondary endpoint 2 TSS:**

For the secondary endpoint 2 of TSS, if more than 50% of the items are missing in the questionnaire, the total scale score will not be computed for the individual (Varni et al., 2011). If the missing data are caused by the missed submission of the PedsOL survey from caregivers, under the scenario of MCAR, the analysis will be performed using complete data. If MAR is assumed, a multiple imputation method will be used to impute missing data based on the relationships between the missing data and other observed variables. If the missing data are MNAR, then pattern mixture models will be used in imputation and inference.

**Secondary endpoint 3 PM2.5:**

For the secondary endpoint 3 of PM2.5, the UM team has developed a protocol to handle the missing data. Multiple steps have been used to identify, flag, and filter out missing data. Briefly, the analysis for secondary endpoint 3 will include participants who return the PurpleAir monitor(s) or have available WiFi hotspot data. If the monitoring time is less than 18 hours per day, the PM2.5 data of the day will not be included in the average weekly PM2.5 calculation.

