9.4.2 ANALYSIS OF THE PRIMARY EFFICACY ENDPOINT

- **Primary Objective:** To test the efficacy of a HEPA filtration unit home intervention, relative to the control arm, with respect to respiratory symptom burden (as measured by symptom-free days; SFD) over 24 weeks following activation of filtration.
- **Primary Endpoint:** Number of caregiver-reported SFDs over 24 weeks following activation of filtration (SFD defined as a 24-hour period without coughing, wheezing, or trouble breathing)
- **Statistical Hypothesis:** Mean of SFDs in the HEPA filtration home intervention group is larger than mean of SFDs in the control group. The hypothesis testing is the comparison of superiority.
- **Statistical Procedures:** The hypothesis will be tested using a mixed effect model after accounting for within cluster correlation. The model uses the primary endpoint as the dependent variable, and the intervention effect (intervention vs. control) as the independent variable or the fixed effect with site as a random effect.
- **Missing Data:** The primary endpoint will be imputed if there is any missing observation in the ITT. The statistician will assess the missing patterns to determine if the cause of missing is missing at random (MAR), missing completely at random (MCAR), or missing not at random (MNAR). Imputation methods such as multiple imputation (MI) methods and pattern-mixture methods will be used in imputation and analyses.

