9.4.3 ANALYSIS OF THE SECONDARY ENDPOINTS

- **Secondary Endpoint 1:** Caregiver reported unscheduled healthcare visits. The proposed statistical method will be a generalized mixed effect model. The dependent variable will be counts of unscheduled health care visits from each of the metrics or the sum of all metrics. Each variable of counts is considered to follow a negative binomial distribution and its log link will be used to connect the independent variable, or the fixed effect of intervention effect with site as a random effect.
- **Secondary Endpoint 2:** Total PedsQLTM Infant Scales score. The proposed statistical model will be a mixed effect model using Total PedsQL score as the dependent variable, the intervention effect as the fixed effect, with site as a random effect. Means (and SEs) of Total PedsQL score estimated from the mixed effect model will be presented in the final result and compared between groups through a p-value to reach a statistical conclusion of significance and superiority.
- **Secondary Endpoint 3:** PM2.5 levels. The proposed statistical model will be a mixed effect model using PM2.5 level as the dependent variable, and the intervention effect as the fixed effect, and site as a random effect. Means and SEs of PM2.5 level from the mixed effect model will be presented in the final result. A p-value of the difference of means between groups will be used to reach a statistical conclusion of significance and superiority.
- **Missing Data:** Missing data of secondary endpoint will be assessed of causes of missing and imputed in analyses, following the same methods proposed for the primary endpoint.

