## **4. Analysis Populations**

### **4.1. Intent-to-Treat Population**

Intent-to-Treat (ITT) Population: The ITT population will include all participants who are randomized to either HEPA filtration (intervention group) or inactive filter unit (control group).

The primary set of analyses for this study will be based on ITT population. A separate analysis will be done with the Per-Protocol population.

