### **SOURCE OF MISSING DATA**

Missing observations of primary endpoint of SFDs can occur if a caregiver fails to 1) complete and submit the weekly symptom survey in a week or in multiple weeks, or (2) complete all symptom questions in a weekly survey.

Missing observations of the secondary endpoint 1 of UHVs can occur if a caregiver fails to 1) complete and submit the weekly survey of healthcare visits in a week or in multiple weeks, or 2) report the counts of ED or UC visits and other medical visits for breathing problems.

Missing observations of the secondary endpoint 2 (total QOL score or TSS) can occur if a caregiver fails to complete and submit the PedsQL survey, or (2) complete all items in the PedsQL questionnaire.

Missing observations of the secondary endpoint 3 of PM2.5 can occur if (1) the PurpleAir monitor fails to function and read the air quality properly, (2) the child's family disables the PurpleAir monitor(s) intentionally or unintentionally, or (3) the participant does not return the PurpleAir monitor(s) and no WiFi hotspot data is available.

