### **HANDLING MISSING DATA**

[figure not shown]
The patterns of missing will be inspected to determine if the missing data are missing completely at random (MCAR), missing at random (MAR), or missing not at random (MNAR). Under the scenario of MCAR, the analysis will be performed using complete data or mean imputation.

When MAR is assumed, a multiple imputation method will be used to impute missing data based on the relationships between the missing data and other observed variables. If the missing data are MNAR, then pattern mixture models will be used in imputation and inference (Little & Wang, 1996).

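### The protocol imputes missing PM2.5 in the ITT set but the SAP describes an available-data analysis; if monitor gaps cluster in weeks when the HEPA unit is off, the PM2.5 reduction may be overstated

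*SAP*

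**What the plan says.** Protocol 9.4.3 (Missing Data) says missing secondary-endpoint data will be "imputed in analyses, following the same methods proposed for the primary endpoint". The method it borrows is in protocol 9.4.2: "The primary endpoint will be imputed if there is any missing observation in the ITT", with multiple imputation and pattern-mixture methods named. SAP 4.1 adds: "The primary set of analyses for this study will be based on ITT population".

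SAP 6.8 then speaks twice. Its general rule, under Handling Missing Data, is not tied to an endpoint: "When MAR is assumed, a multiple imputation method will be used to impute missing data", with pattern-mixture models if data are missing not at random. Its PM2.5 paragraph says something else: "Multiple steps have been used to identify, flag, and filter out missing data", and "the analysis for secondary endpoint 3 will include participants who return the PurpleAir monitor(s) or have available WiFi hotspot data". It also leaves a day out of the weekly average "If the monitoring time is less than 18 hours per day". No imputation is mentioned there.

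The neighbouring paragraphs are explicit. For healthcare visits, SAP 6.8 rules out statistical imputation and gives a reason. For quality of life, it repeats multiple imputation. The PM2.5 paragraph does neither. SAP section 7, where departures from the protocol must be described and justified, contains only its template sentence.

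**The concern.** Weekly PM2.5 is the trial's evidence that the assigned intervention lowered exposure over 24 weeks, and the symptom result will be read against it. Two analyses are open, and the documents do not say which one is reported.

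The choice could change the estimate because of how gaps may arise. SAP 6.8 lists among the causes of missing PM2.5 that the "family disables the PurpleAir monitor(s) intentionally or unintentionally". Filter unit and monitor stand in the same rooms (protocol 1.3, footnote 4), and both need mains power. If some families switch off both, the weeks lost in the HEPA arm are weeks without filtration. Losing unit-off weeks in the control arm changes little, because control units hold no filters (protocol 6.1.1). The available weeks would then describe exposure while the filter runs, rather than exposure over the 24 weeks as assigned. A null symptom result could be set against a larger exposure contrast than the children received.

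The model for this endpoint in SAP 6.6.2 names no weekly unit use, although the weekly survey records use and setting by room (protocol 8.1).

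**Working it through.** **Plan's own figures.** The documents give no expected effect, variance or missing-data rate for PM2.5. Their only power figure is for symptom-free days: 20/43 × √(98/2) = 3.256, and Φ(3.256 − 1.960) = 90.2% (90.0% with the t distribution). This matches the stated 90% but has no bearing on the present point.

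**Inputs.**
- r = 50%, the reduction while the filter runs. Protocol 2.1 and 2.2 report at least this in most studies.
- q, the share of HEPA-arm weeks with the unit off. Assumed, 5% to 30%.
- m_off and m_on, the shares of filter-off and filter-on weeks without monitor data. Assumed.

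**Formulas** (reduction relative to control):
- All weeks: r(1 − q)
- Available weeks: r(1 − q)(1 − m_on) / [(1 − q)(1 − m_on) + q(1 − m_off)]

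With q = 20%, m_off = 50% and m_on = 0, the all-weeks value is 0.5 × 0.8 = 40%. The available-weeks value is 0.40 / (0.80 + 0.10) = 44.4%. Only 10% of home-weeks are missing.

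| Unit off (q) | All weeks | m_off 50%, m_on 0 | m_off 100%, m_on 0 | m_off 10%, m_on 30% |
|---|---|---|---|---|
| 5% | 47.5% | 48.7% (+1.2) | 50% (+2.5) | 46.8% (−0.7) |
| 10% | 45% | 47.4% (+2.4) | 50% (+5.0) | 43.7% (−1.3) |
| 20% | 40% | 44.4% (+4.4) | 50% (+10.0) | 37.8% (−2.2) |
| 30% | 35% | 41.2% (+6.2) | 50% (+15.0) | 32.2% (−2.8) |

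Brackets give the difference in percentage points. When m_on = m_off the difference is zero. When r = 0 both formulas give zero.

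**Size against the standard error** (q = 20%, m_off = 50%, m_on = 0, log scale). The true effect is ln(0.5) × 0.8 = −0.555. The available-weeks effect is ln(0.5) × 0.889 = −0.616. The shift is about −0.06. Assume 98 homes per arm, a between-home SD of 0.5 and a weekly SD of 0.4. With 24 × 0.9 = 21.6 observed weeks per home, each home mean has variance 0.25 + 0.16/21.6 = 0.257. Switching adds about 0.002 in the HEPA arm. The SE is √[(0.257 + 0.259)/98] ≈ 0.073, and simulations gave 0.072 to 0.074. The shift is therefore 0.8 to 0.9 of the SE. If use varies between homes the shift is smaller; simulated values ran from 0.036 to 0.062.

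**Does imputation remove it?** With q = 20%, m_off = 80% and m_on = 5%, available data give 0.38/0.80 = 47.5% against a true 40%. In a large simulation of this case, available data gave 47.4%, imputation by arm alone 47.4%, and imputation by arm and reported use 39.9%. The correction comes from the unit-use information.

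**The case against.** A reader might infer that the reported PM2.5 reduction will be too large. The documents do not support that. Nowhere do they say that filter and monitor are unplugged together; SAP 6.8 mentions disabling the monitor without mentioning the filter. The reasons protocol 5.5 reports for switching filters off are noise and electricity cost, which are complaints about the filter. Families who stop the unit may complete the remaining procedures (protocol 7.1) and are asked about continuing air-quality measurement (7.2). SD cards cover WiFi gaps, the survey asks weekly whether the monitor is on, and its return is paid. Protocol 5.5 also reports strong compliance with a similar unit, although it notes declining use in some other studies. At 90% to 95% use with half of the off weeks lost, the overstatement is only 2.4 to 1.2 points.

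The PM2.5 paragraph is also expressly brief and summarises a separate procedure. The 18-hour rule is a completeness criterion, and the general imputation rule may still apply. So one cannot conclude that imputation was abandoned, only that the texts do not agree.

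Finally, the test is hardly threatened: in the illustration the effect is −0.55 or −0.62 log units with an SE of about 0.07.

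All of this stands. It limits the certainty, direction and size of any bias. It does not settle which analysis is planned, nor explain the empty section 7.

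**Conclusion.** The inconsistency holds. Protocol 9.4.2 and 9.4.3 call for imputation of PM2.5 in the ITT set, the SAP's PM2.5 paragraph describes an available-data analysis, the SAP's general rule sits between them, and no departure is recorded.

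Bias is a conditional risk. It requires monitor gaps to be more common in filter-off weeks of the HEPA arm, and the documents give no rate for that. Under the illustrative assumptions above, the result is 44% against 40%. Across the assumptions shown, the difference runs from 2.8 points too small to 15 points too large, the latter only if 30% of weeks are filter-off and all of them are unmonitored. The size of the reduction is at stake, while a false positive from this mechanism is not.

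It would also be wrong to infer that restoring protocol 9.4.3 is sufficient. That section does not specify unit use in the imputation, and imputing by arm alone reproduces the available-data answer. For a secondary exposure endpoint this is a worthwhile and inexpensive improvement.

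**What to change.** 1. Reconcile the PM2.5 paragraph of SAP 6.8 with protocol 9.4.3 and with the SAP's general rule, and record any remaining departure, with its reason, in SAP section 7.
2. Report PM2.5 missingness by arm and by caregiver-reported unit use.
3. Add an ITT analysis that multiply imputes missing weekly PM2.5 by room, using arm, reported unit use and setting, arm-by-use, baseline PM2.5, outdoor PM2.5 and the home's other weeks. Show it beside the monitor-available analysis.
4. Add a missing-not-at-random variant that sets missing HEPA-arm weeks to control-like levels, for weeks that lack both survey and monitor data. Disengaged families may skip both, and there the imputation in item 3 is weakest.

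The cost is SAP wording, some extra analysis on data the protocol already collects, and slightly wider intervals.

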**7. Changes to SAP**

*Any changes to the statistical approaches described in protocol must be described here with justification.*

